Power and Statistical Analysis: We will analyze in an intent-to-treat (ITT) manner such that all participants, regardless of whether they complete the intervention, will be invited to return for the follow-up sessions and will be included in primary analyses. Secondary analyses will be conducted using a per-protocol approach, which restricts the analysis to the participants that completed the intervention. All cognitive and neuroimaging data will be interrogated for normality and any non-normal data will be transformed. Any data that cannot be transformed will be analyzed using non-parametric tests. Non-parametric regression models will be used for continuous variables when necessary. Outlier de-weighting will be conducted to remove the influence of anomalous data. All analyses will be two-tailed. We will first summarize baseline demographic and brain characteristics of the sample and intervention groups by conducting Pearson, Spearman, and Chi-square statistics as appropriate. Our primary goals are to examine whether the intervention improves cognitive and brain health. To test these hypotheses, we propose to use a General Linear Mixed Model (GLMM) in standard neuroimaging and statistical packages. Effects of Time (baseline, 6-month), Group (Dance, Education), and Time by Group interactions will be examined. Post-hoc comparisons using least square means will decompose any significant interactions and will be plotted to illustrate the direction of the effect. Mean differences between groups for all cognitive and neuroimaging outcome measures will be derived using linear contrasts and multiple comparisons will be corrected by standard protocols. Differences in baseline characteristics will be accounted for by using covariance adjusted models.

We will describe differences in baseline characteristics between participants with complete versus incomplete follow-up to assess any bias (e.g., age) in those who do not return for follow-up. However, according to ITT analyses, all participants including those that do not complete the intervention will be analyzed as part of the trial. Using hierarchical regression models, we will be able to explore whether changes in any cognitive or neuroimaging metric (e.g., white matter integrity) varies as a function of improvements in PA or fitness independently of assigned group. We also appreciate that there will be significant individual variability in factors such as body mass, blood pressure, fitness level, or SES. Instead of modeling this variation as ‘noise’ we plan to take advantage of the variability to further explore, independently of group assignment, the associations between cognitive and brain imaging metrics and initial levels and individual change trajectories. Main effects and interaction terms will be modeled in these regression analyses and time-dependent changes will be explored and illustrated by scatter plots. These analyses will be useful for generating future hypotheses and questions.

Power Analyses: Our proposed sample size of 180, with randomization of 90 participants in each group, is based on effect sizes from preliminary data. Even when accounting for attrition and retention of ~70% of participants (65 in each group), we are sufficiently powered to detect effects in cognitive and brain outcomes and to test for mediation.

Cognitive performance: Our prior PA interventions have found moderate sized effects on cognitive function after 6-months with a Cohen’s d ranging from 0.40 to 0.80 depending on the outcome. In our analysis of the pilot data from the African Dance intervention with only 19 participants (9 in the Dance group) we estimate similar or greater effect sizes of ~.70. If we estimate an effect of 0.70, 65 participants per group after attrition will provide us with >91% power to examine our primary hypotheses.

Brain volumetrics: Our prior 6-12 month PA interventions have used between 30 and

60 subjects per group with Cohen's d ranging between 0.40 and 0.50 using similar analysis approaches. Cross-sectional research has reported significant effects of PA on brain volume with only 32 subjects and effect sizes between 0.50 – 0.60. Preliminary data on 37 African Americans from one of our prior studies suggest that cross-sectional differences between African Americans engaging in PA compared to those not engaging in PA are larger than for whites (Cohen's d = 1.83). These studies argue for a moderate-to-large effect of PA on brain volume depending on the sample, the measure of PA and fitness, and the brain metric used. If we estimate a conservative effect size of 0.50, 65 participants per group will be sufficient to detect differences in brain volume at 81% power.

Diffusion tensor imaging: Changes in white matter have been detected in PA interventions in as little as 6-months with only 50 subjects. In a 12-month PA intervention, we found increased FA with only 35 subjects in each group with an estimated effect size of 0.70. Based on an estimated effect size of 0.75, we should have >85% power with 65 participants per group to test our main hypotheses as well as enough power for exploratory analyses.

Task-evoked activity: Task-evoked brain imaging studies of PA have found statistically significant effects with 30 - 50 subjects per group with effect sizes ranging between 1.0 and 1.3 depending on the region examined and the task employed. Cross-sectional studies of fitness on brain activity report even larger effects up to 1.70. These patterns indicate a large effect size of PA on brain function, so 65 participants per group will provide us with substantial power to test our main aims and hypotheses.

Connectivity: With only 65 people, we have shown that a PA intervention is effective at enhancing functional connectivity in prefrontal-inhibitory networks. The difference between the groups for prefrontal cortex connectivity was .15 with a standard deviation of .10 suggesting an effect size of 1.5 (Cohen's d). Therefore, similar to the effect sizes and power for the other measures, 65 participants per group should be sufficient for detecting changes as a function of the intervention with >85% power.

Given the continued challenges of navigating the COVID-19 pandemic, we requested to modify our recruitment/randomization accrual and targeted sample size for the study titled "Rhythm Experience and Africana Culture Trial (REACT II)" on August 29th, 2023. We have determined that we will have sufficient statistical power to test our primary aims with a reduction in the targeted sample size from 180 to 150.

The recommended changes were approved by the meeting of the Data Safety and Monitoring Board on August 29, 2023.

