- History of severe head trauma, major stroke, or brain tumors

- History of psychiatric disorders other than past major depressive episodes or anxiety
- History of falls or other balance problems
- History of heart or cardiovascular disease, including heart failure, angina, or hypertension not currently controlled by medication (i.e., exceeding 190/100).
- Unable to complete submaximal fitness test

1.7.3 Baseline Testing.

There are several outcome measurement sessions at baseline (Cognitive, Fitness/Blood, and MRI sessions) which must be completed prior to randomization. It will be recommended that all assessments happen within a 6-week window that starts the day the informed consent document is signed at session 1. However, given challenges with scheduling and safety clearances that may be necessary in older adults, we will work to collect all baseline data on participants, even if the session exceeds the 6-week window.

Session 1: Participants will come to the laboratory and complete a battery of cognitive and neuropsychological tests (see below for a description of the tests). Compliance with the test instructions will be monitored by a study certified administrator. Participants will be allowed to take breaks between tests on a regular basis to help reduce fatigue. The cognitive tasks to be completed during the cognitive session are described in more detail below. The tasks can be grouped into several broad cognitive categories:

- *General Cognition:*
 1. MOCA (Montreal Cognitive Assessment): was designed as a rapid screening instrument for mild cognitive dysfunction. It assesses different cognitive domains: attention and concentration, executive functions, memory, language, visuoconstructional skills, conceptual thinking, calculations, and orientation. Time to administer the MoCA is approximately 10 minutes. The total possible score is 30 points; a score of 26 or above is considered normal.
 2. Wechsler Test of Adult Reading (WTAR): estimates pre-morbid intellectual functioning (approximate intelligence). This test takes approximately 5 minutes to administer and will only be administered at the baseline testing session.
- *Working Memory:*

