- Hippocampal subfield sequence
- DSI (Diffusion Spectral Imaging)
- FLAIR
- pCASL

If the research team discovers an incident or abnormality (e.g., tumor) as a part of the MRI scan, it is important for the study subject to be informed (a) that these scans were not designed for clinical purposes and so a clear diagnosis and prognosis cannot be made, but (b) that if an incidental finding or abnormality is found in the scan that we will follow standard procedures of the MRI center which includes the consultation of a board certified neuroradiologist at the University of Pittsburgh. The consultation would involve an assessment of the scan and the neuroradiologist would provide feedback to the Principal Investigator to pass along to the subject. This may require the Principal Investigator to recommend that the subject inform their personal physician about the abnormality and request follow-up procedures that are outside the purview of the research study.

1.7.4 Post-Randomization Tasks. The self-efficacy questionnaire will be completed during the third week of the intervention. In addition, the physical activity monitoring device will be worn for one week, every 6 weeks for the duration of the study.

1.7.5 Follow-up Testing (6 months). After 6-months of the intervention sessions, the participants will complete one cognitive assessment similar to that of the baseline visit. The tasks will be the same as those described above but will not include the WTAR or the Health History questionnaire. This time point also includes a blood draw to collect the same biomarkers as the Time point 1 blood draw.

1.7.6 Blinding of Study Staff. All study staff administering the outcomes assessment sessions will be blinded to participants' group assignments. Given this, special planning is in place to ensure adequate staffing for both the pre- and post- assessments.

1.9 RANDOMIZATION:

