After the completion of the measures and sessions described above the participants will be randomly assigned to one of two groups: (a) The Dance condition will consist of approximately 180 minutes per week of moderate intensity African Dance, or (b) an Africana Culture control condition that will consist of 180 minutes per week of mixed-programming related to African Culture, including art projects, cooking, and films. We will use a computer randomization protocol that will incorporate a verification that all session visits have been completed and data entered into the database. We will use a stratified permuted block randomization algorithm with equal allocation to one of the two groups. The use of this strategy will ensure treatment balance on the two factors of age at study entry ($=<70, >70$) and gender. Once randomized, an assigned staff member will contact the subject via phone with the group information. On this contact, the staff

member will give information such as date, day, time, and location of the subject's first intervention session.

1.10 EXERCISE INTERVENTION GROUPS:

1.10.1 African Dance Group. Participants in the Dance condition will begin by dancing at reduced intensity during the first week of the program and will gradually increase their dancing intensity each subsequent week until they reach 40-60% of their heart rate reserve for all of the dance class. All dance sessions start and end with 5-10 minutes of active stretching for the purpose of warming up and cooling down. As the participants will be low active at baseline, the prescribed intensity will be 50–65% of the maximum heart rate reserve for weeks one to four and 65–80% for the remainder of the program. Participants will be fitted with a Polar Bluetooth Smart heart rate sensor around their chest and be encouraged to dance within their target heart rate zone by fitness staff. Continuous heart rate readings of all participants will be displayed in real-time via the Polar Team app on an iPad or other tablet. Certified exercise instructors will closely monitor attendance, intensity, frequency, and safety. Dance sessions will occur three days/week at one of two study sites for the duration of the intervention.

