1.11 ANALYSIS PLAN

Our analysis plan has proposed an intent-to-treat analysis where all participants, regardless of whether they complete all sessions, will be invited to return for follow-up assessments. However, there will likely be some participants that refuse to return for follow-up assessments. “Lost to follow up” will be defined here as missing data that is contributing to the primary outcomes (executive functioning and hippocampal volume). The reason will be recorded (i.e., missed visit due to traveling, illness). These criteria and documentation will also be applied for any discontinued subjects with the reasons for discontinuation being recorded (i.e., moving out of state).

We propose to use all available data in the planned analysis for testing our primary outcomes. We will assess the missingness of data consistent with the assumptions of the modeling approach described above. That is, we will examine the randomness of missing data and examine if the data is missing completely at random (MCAR) or missing at random (MAR). Parameters of the GLMM will be estimated using the maximum likelihood estimation or restricted maximum likelihood methods that are known to produce consistent and efficient estimates under MAR.

Imaging data analysis. We will first analyze each imaging outcome (e.g., volume) separately from every other imaging outcome (e.g., fMRI). But, once voxel-wise associations related to the intervention are established, we could test, using hierarchical regression, the relative significance of each imaging measure to explain improvements in cognitive function with the intervention.

1.12 PARTICIPANT SAFETY:

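### The primary Time-by-Group model leaves the arms free to differ at baseline; a common baseline mean, justified because baseline precedes randomisation, would be somewhat more precise at no cost

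*Combined protocol and SAP*

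**What the plan says.** The primary model appears in identical terms in protocol section 1.3.1 (General Approach) and in the SAP under Power and Statistical Analysis: "Effects of Time (baseline, 6-month), Group (Dance, Education), and Time by Group interactions will be examined". Baseline is therefore a response value, and the Group term lets the arms have different means at that visit.

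Both places then add: "Differences in baseline characteristics will be accounted for by using covariance adjusted models". No covariate is named, and the baseline value of the outcome is not mentioned. Section 1.3.1 further says that covariates found to be significantly associated with missingness will enter the models for the primary tests.

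Other relevant statements:

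- Section 1.7.3: "There are several outcome measurement sessions at baseline (Cognitive, Fitness/Blood, and MRI sessions) which must be completed prior to randomization". The MRI list there includes the "Hippocampal subfield sequence".
- Section 1.9, on the stratified permuted blocks: "The use of this strategy will ensure treatment balance on the two factors of age at study entry" (cut at 70) and gender. Neither factor appears in any model description.
- Section 1.11 names the "primary outcomes (executive functioning and hippocampal volume", calls for ML or REML estimation, and states: "We propose to use all available data in the planned analysis for testing our primary outcomes".
- Section 1.3.1 and the SAP, on intention to treat: "all participants including those that do not complete the intervention will be analyzed as part of the trial".
- The closing note of the SAP cuts the target from 180 to 150.

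**The concern.** Because the baseline sessions precede allocation, the arms have equal expected baseline means by design. A model that estimates a separate baseline mean for each arm spends information on a difference known to be zero in expectation. Fixing that difference at zero leaves the treatment estimate unbiased and reduces its variance whenever the two visits correlate at less than 1.

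The wording also leaves an analyst a choice. Free arm means at baseline, a common baseline mean, and baseline entered as a covariate can each be defended from the text, and they give different standard errors. The last, if fitted only to participants with a 6-month value, would drop the others and conflict with the commitment to analyse everyone.

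Precision matters more since the target was cut. Retention of about 70% of 75 per arm leaves roughly 52 completers, against the 65 behind the stated power.

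**Working it through.** **Reproducing the plan's figure.** For brain volume the SAP states 81% power at d = 0.50 with 65 per group. A two-sided two-sample t test at 5% gives 80.8% (normal approximation 81.3%). The documents state two-tailed tests but no alpha level, so 0.05 is assumed. This calculation contains no correlation between visits, so it does not reveal which baseline handling was intended.

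**Inputs.**

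- N = 75 randomised per arm: 150/2, with equal allocation (SAP closing note; section 1.9).
- n = 52 completers per arm: 0.70 × 75 = 52.5, rounded down (section 1.3.2 and SAP, Power Analyses).
- Outcome SD = 1 at both visits (assumed).
- r, the baseline-to-6-month correlation, is not in the documents; 0.5 to 0.9 is shown.

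**Large-sample variance of the treatment contrast, using all available data.**

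- Free arm means at baseline: V_free = 2[(1 − r²)/n + (1 − r)²/N]
- Common baseline mean: V_common = 2(1 − r²)/n

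**Power.** The documents do not say what SD standardises d. Taking d in SDs of change, the difference is δ = d√(2(1 − r)), and power = Φ(δ/√V − 1.96).

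**Worked case, r = 0.7, d = 0.50.** (1 − 0.49)/52 = 0.009808 and 0.09/75 = 0.001200. V_free = 2 × 0.011008 = 0.02202; V_common = 2 × 0.009808 = 0.01962. The cut is 1 − 0.01962/0.02202 = 10.9%. δ = 0.50 × 0.7746 = 0.3873. Power is Φ(0.3873/0.1484 − 1.96) = 74.2% with free means and Φ(0.3873/0.1401 − 1.96) = 79.0% with a common mean.

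| r | V_free | V_common | Variance cut | Same as extra participants | Power, d = 0.50 | Power, d = 0.70 |
|---|---|---|---|---|---|---|
| 0.5 | 0.03551 | 0.02885 | 18.8% | 23% | 75.6 → 83.7% | 96.0 → 98.5% |
| 0.6 | 0.02888 | 0.02462 | 14.8% | 17% | 74.9 → 81.3% | 95.8 → 97.9% |
| 0.7 | 0.02202 | 0.01962 | 10.9% | 12% | 74.2 → 79.0% | 95.5 → 97.2% |
| 0.8 | 0.01491 | 0.01385 | 7.2% | 8% | 73.6 → 76.7% | 95.2 → 96.4% |
| 0.9 | 0.00757 | 0.00731 | 3.5% | 4% | 72.9 → 74.4% | 94.9 → 95.6% |

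Using the plan's own 65/90 retention (54 completers of 75), the cuts are 19.4, 15.3, 11.3, 7.4 and 3.7%.

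**If d is in SDs of the raw outcome** (δ = d), power at d = 0.50 goes from 75.6 to 83.7% (r = 0.5), 83.7 to 89.0% (0.6) and 92.1 to 94.6% (0.7), with no real gain at 0.9.

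**Simulation checks.**

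- Bias: 20,000 trials with 90 randomised and 65 completers per arm, r = 0.6, true effect 0.50. Mean estimates were 0.499 (free) and 0.500 (common), with SEs 0.152 and 0.140. The variance ratio was 0.854, against 0.847 from the formulas.
- Type I error: 8,000 trials per setting with 76 randomised and 52 completers per arm, at r = 0.5 and 0.7. It was 5.1 and 4.8% with free means, 5.0 and 5.4% with a common mean (Monte Carlo error about ±0.5 point).
- Strata: adding them to the common-mean model at r = 0.7, raw-SD effect 0.50, moved power from 93.7 to 93.5% (strata with no effect), 95.7 to 95.6% (strata explaining 10% of level) and 93.2 to 93.9% (strata explaining 5% of change).

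**The case against.** The strongest reply is that nothing here is an error. Time, Group and Time by Group fitted by ML or REML to all available data is a standard, unbiased analysis. That stands. A reader might infer from free baseline means that the planned test is biased or has the wrong size; neither the documents nor the simulations support that.

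A reader might also infer that baseline handling is left wholly unstated. That goes too far. Baseline is explicitly a level of Time. The phrase about baseline characteristics could even cover baseline brain measures, since both documents speak of summarising baseline brain characteristics shortly before. What stays open is whether arm means are constrained at baseline and whether the adjustment sentence includes the baseline outcome.

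The most tempting overstatement is that a common mean restores the power lost by the cut to 150. The 8-point gain needs d = 0.50 together with r = 0.5. In the plan, 0.50 is the brain-volume effect, and hippocampal volume may well be highly repeatable; at r = 0.8 to 0.9 the gain is about 1 to 3 points. For cognition the planning value is 0.70, where power is already about 95%. A larger cognitive gain would need an effect nearer the bottom of the plan's quoted 0.40 to 0.80 range. Under raw-SD units and r of 0.6 or more, the free-mean model already exceeds the planned 81% with 150 randomised. All of this limits the size of the point without removing it.

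Finally, the omission of the strata might be read as a loss of power. The simulated changes are under 1 point and go both ways, so it should not be.

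**Conclusion.** The point holds as one of specification and efficiency. As written, the primary model is valid but estimates a baseline difference that the design sets to zero in expectation. A common baseline mean removes between 3.5 and 19% of the variance of the treatment contrast over r = 0.9 to 0.5. Matched to the plan's own effect sizes, that means at most about 2.5 points of power for cognition at d = 0.70, and 1 to 3 points for hippocampal volume if it is highly repeatable (r = 0.8 to 0.9).

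These figures assume a 5% two-sided test, equal SDs at both visits, 75 randomised and 52 completers per arm, and d in SDs of change. The correlation is an assumption throughout. Low to moderate priority: no bias or type I error is being corrected.

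**What to change.** Make the change before outcome data are seen by arm, and record the date. In section 1.3.1 and in the SAP under Power and Statistical Analysis, state that:

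- the primary model is fitted by REML to all randomised participants, with baseline and 6-month values as responses and an unstructured covariance for the two visits;
- the baseline mean is common to both arms (terms Time and Time by Group, no Group difference at baseline), and the treatment effect is the Time-by-Group contrast at 6 months;
- age group (70 or under, over 70) and gender, each with its interaction with Time, are included because allocation was stratified on them, with no power gain claimed;
- participants without a 6-month value stay in the model, as section 1.11 and the SAP commit to, so a baseline-as-covariate model restricted to completers is not substituted;
- covariates chosen from observed baseline differences, or from an observed association with missingness, are used in sensitivity analyses only.

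The cost is wording in two places. Baseline cognitive scores, baseline MRI, age and gender are already collected, and no visit or procedure changes.

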Aim 3 proposes to explore physiological and socioemotional mechanisms of the dance intervention. We plan to explore our hypotheses using several different approaches including simple mediational models applying the change score method and will estimate whether the dance intervention (predictor) on *changes* in cognitive function outcomes are mediated through *changes* in the suspected mediators. Goodness-of-fit will be assessed through standard summary indices (e.g., RMSEA, CFI) and model assessment via residual analyses will be performed. Total, indirect and direct effects will be estimated. Additionally, we will explore mediation applying the half-longitudinal approach proposed by Cole and Maxwell as well as an autoregressive mediational approach. Finally, we will explore recent advancements in repeated measures mediation analyses developed by Preacher and Hayes. Depending on the results from simple mediational modeling, we may also combine mediators into a multiple mediator model to develop a more comprehensive picture of these pathways.

1.3.2 Power Analyses. Our planned sample size of 180, with randomization of 90 participants in each group, is based on effect sizes from preliminary data. Even when accounting for attrition and retention of ~70% of participants (65 in each group), we are sufficiently powered to detect effects in cognitive and brain outcomes and to test for mediation.

1.3.3 Cognitive performance. Our prior PA interventions have found moderate sized effects on cognitive function after 6-months with a Cohen’s d ranging from 0.40 to 0.80 depending on the outcome (23). In our analysis of the pilot data from the African Dance intervention with only 19 participants (9 in the Dance group) we estimate similar or greater effect sizes of ~.70. If we estimate an effect of 0.70, 65 participants per group after attrition will provide us with >91% power to examine our primary hypotheses.

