1.3.4 Brain Volumetrics. Our prior 6-12 month PA interventions have used between 30 and 60 subjects per group with Cohen's d ranging between 0.40 and 0.50 using similar analysis approaches (18, 20, 27, 41, 42). Cross-sectional research has reported significant effects of PA on brain volume with as few as 32 subjects and effect sizes between 0.50 – 0.60 (24, 40, 42–44). Preliminary data on 37 African Americans from one of our prior studies suggest that cross-sectional differences between African Americans engaging in PA compared to those not engaging in PA are larger than for whites (Cohen's d = 1.83). These studies argue for a moderate-to-large effect of PA on brain volume depending on the sample, the measure of PA and fitness, and the brain metric used. If we estimate a conservative effect size of 0.50, 65 participants per group will be sufficient to detect differences in brain volume at 81% power.

1.3.5 Diffusion tensor imaging. Changes in white matter have been detected in PA interventions in as little as 6-months with only 50 subjects (45). In a 12-month PA intervention, we found increased FA with only 35 subjects in each group with an estimated effect size of 0.70 (41). Based on an estimated effect size of 0.75, we should have >85% power with 65 participants per group to test our main hypotheses as well as enough power for exploratory analyses.

1.3.6 Task-evoked activity. Task-evoked brain imaging studies of PA have found statistically significant effects with 30 - 50 subjects per group with effect sizes ranging between 1.0 and 1.3 depending on the region examined and the task employed (26). Cross-sectional studies of fitness on brain activity report even larger effects up to 1.70 (36, 46, 47). These patterns indicate a large effect size of PA on brain function, so 65 participants per group will provide us with substantial power to test our main aims and hypotheses.

1.3.7 Connectivity. With only 65 people, we have shown that a PA intervention is effective at enhancing functional connectivity in prefrontal-inhibitory networks (27). The difference between the groups for prefrontal cortex connectivity was .15 with a standard deviation of .10 suggesting an effect size of 1.5 (Cohen's d). Therefore, similar to the effect sizes and power for the other measures, 65 participants per group should be sufficient for detecting changes as a function of the intervention with >85% power.

1.7 PROCEDURES:

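### The brain-volume power statement calls d = 0.50 conservative although it is the upper end of the group's own interventional range, and its 81% rests on 65 per arm from the superseded target of 180

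*Combined protocol and SAP*

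**What the plan says.** The brain-volume paragraph is nearly identical in protocol 1.3.4 and in the SAP under Brain volumetrics. It draws on three sources of effect size.

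- **The group's own 6- to 12-month activity interventions.** The SAP says these used between 30 and "60 subjects per group with Cohen's d ranging between 0.40 and 0.50 using similar analysis approaches". Protocol 1.3.4 gives the same range.
- **Other literature.** "Cross-sectional research has reported significant effects of PA on brain volume with only 32 subjects and effect sizes between 0.50 – 0.60".
- **A contrast in 37 African Americans from a prior study.** Differences between those "engaging in PA compared to those not engaging in PA are larger than for whites (Cohen's d = 1.83"). The plan labels this contrast cross-sectional too.

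The plan concludes: "If we estimate a conservative effect size of 0.50", then 65 per arm is enough to show a brain-volume difference with 81% power. No brain-volume power is given for a smaller effect.

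The 65 comes from the general power paragraph (protocol 1.3.2 and the SAP under Power Analyses). The SAP states there: "Our proposed sample size of 180, with randomization of 90 participants in each group, is based on effect sizes from preliminary data". Both documents then allow for "retention of ~70% of participants (65 in each group").

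The closing note of the SAP, dated 29 August 2023, lowers the target from 180 to 150. It says that power for the primary aims remains sufficient but gives no figure. Protocol 1.11 names executive functioning and hippocampal volume as the primary outcomes.

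**The concern.** A conservative planning value normally sits towards the low end of the relevant evidence. For a randomised comparison of dance with a culture class, the most relevant evidence is what earlier interventions achieved. On the plan's own account that is 0.40 to 0.50, so the chosen value is the most favourable in that range.

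The number analysed has also moved. The 65 per arm follows from 90 randomised per arm, and the current target implies 75.

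What is at stake is how a null result on a primary outcome would be read. Measured against 81% power at a supposedly cautious effect, it could be taken as good evidence that dance does not change hippocampal volume. If the effect were of the size seen in the group's less favourable interventions, the trial could quite plausibly miss it.

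**Working it through.** **Inputs**

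- d = 0.40 and 0.50: ends of the group's interventional range (protocol 1.3.4; SAP, Brain volumetrics).
- 65 per arm: protocol 1.3.2; SAP, Power Analyses.
- Two-sided testing: protocol 1.3.1 and the SAP.
- Equal allocation: protocol 1.9.
- Target 150: closing note of the SAP.
- *Assumed:* alpha 0.05, because neither document gives a number; about 70% retention carried over to the new target; an unadjusted two-sample t-test.

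**Formula.** With n analysed per arm, the noncentrality is d × √(n/2) on 2n − 2 degrees of freedom. Power is the chance that the noncentral t exceeds the two-sided 5% critical value. The normal approximation is Φ(d√(n/2) − 1.96).

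**Step 1: reproduce the plan's figure.** For n = 65, √(65/2) = 5.701. At d = 0.50, Φ(2.850 − 1.96) = Φ(0.890) = 81.3%; the t-test gives 80.8%. Both agree with the stated 81%. A one-sided 0.05 test would give 88.3% and a two-sided 0.025 test 71.9%, so two-sided 0.05 is evidently the setting used.

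**Step 2: the lower end of the range, same n.** At d = 0.40, Φ(2.280 − 1.96) = Φ(0.320) = 62.6%; the t-test gives 61.9%. The choice between the two ends is worth 80.8 − 61.9 = 18.9 points.

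**Step 3: the current target.** 150/2 = 75 per arm, and 0.70 × 75 = 52.5, so 52 to 53 analysed. For n = 52, √(52/2) = 5.099. At d = 0.50, Φ(2.550 − 1.96) = Φ(0.590) = 72.2%; the t-test gives 71.4%. At d = 0.40, Φ(2.040 − 1.96) = Φ(0.080) = 53.2%; the t-test gives 52.4%.

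| Analysed per arm | Basis | Power at d = 0.40 (t-test) | Power at d = 0.50 (t-test) |
|---|---|---|---|
| 65 | as stated, target 180 | 61.9% | 80.8% |
| 52 | about 70% of 75 | 52.4% | 71.4% |
| 53 | about 70% of 75 | 53.2% | 72.2% |
| 54 | 65/90 = 72.2% of 75 | 54.0% | 73.1% |
| 75 | no attrition, target 150 | 68.2% | 86.0% |

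**Step 4: what 80% would require.** With 52 per arm, 80% power needs d of about 0.55, which is above the whole interventional range. At d = 0.50, 80% needs 64 completers per arm, and 64/75 = 85% retention.

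**The case against.** **The word has a basis in the plan.** The paragraph sets 0.40-0.50, 0.50-0.60 and 1.83 side by side, calls the effect moderate to large, and picks a value near the bottom of that collection. That explains the label. It still leaves 0.50 as the top of the values the plan attributes to the group's interventions, with nothing shown below it.

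**The cross-sectional label may not fit every source.** A reader might infer that 0.40-0.50 is the only randomised evidence offered. The documents do not support so firm a statement. Protocol 1.3.4 cites references 24, 40 and 42-44 for the 0.50-0.60 range. By their titles, reference 44 is a six-month randomised trial and reference 42 an exercise intervention; reference 42 is also cited for the lower range. Which design produced which value cannot be told from the documents. This objection stands, and it is for the sponsor to clarify.

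**The planned model may do better than a t-test.** The plan specifies a mixed model with baseline, covariate adjustment and all available data. If d is scaled by the follow-up standard deviation, adjusting for a baseline with correlation r turns d into d/√(1 − r²). Reaching the 0.555 needed at 52 per arm would take r = √(1 − (0.50/0.555)²) ≈ 0.43 from d = 0.50, or √(1 − (0.40/0.555)²) ≈ 0.69 from d = 0.40. If d is already on the change scale, that gain cannot be counted in this way. The plan gives neither the scale nor a correlation, and its own 81% matches the unadjusted test. So 81% should not be described as a ceiling or best case. In the other direction, the plan promises multiplicity correction, which would lower power.

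**The lowest figures combine several assumptions.** The 52-53% needs the smaller d, the reduced target, equal arms and the carried-over retention all at once. That is fair, and each should be stated alongside the figure.

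**Conclusion.** The point holds as a matter of labelling and of a power figure tied to a superseded target. On the plan's own interventional range, power at 65 per arm is about 62% to 81%, and the plan reports only the upper figure. At the current target of 150 the range is about 52-53% to 71-72%. These figures assume two-sided alpha 0.05, an unadjusted t-test, 1:1 allocation and about 70% retention.

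Two stronger readings are not supported. First, the 81% is not an arithmetic error; it reproduces from its inputs. Second, a reader might count 65 against 70% of 90 = 63 as a mistake. The plan says approximately 70%, 65/90 is 72.2%, and the difference at d = 0.50 is 80.8% against 79.5%, about 1.3 points. By the normal approximation, 63 per arm still gives 80.1%. That is rounding.

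Nor does this show that the trial must enrol more people. It shows that the stated assurance for a domain containing a primary outcome is more favourable than the cited intervention results and the current target support.

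**What to change.** In protocol 1.3.4 and the SAP paragraph on brain volumetrics:

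1. Delete the word conservative and say that 0.50 is the upper end of the range from the group's own interventions.
2. Replace the 81% with power at d = 0.40 and d = 0.50 for the target of 150. Give the alpha, the retention assumed, the scale on which d is defined, and any gain credited to baseline adjustment with the correlation behind it.
3. Either present 0.50-0.60 and 1.83 as supporting background, or state which of them come from interventions.

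Suggested wording, if no baseline gain is credited:

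> Our prior interventions gave d between 0.40 and 0.50 for brain volume. With 150 randomised 1:1 and about 70% retained (52-53 per arm), an unadjusted two-sided test at alpha 0.05 has about 52-53% power at d = 0.40 and 71-72% at d = 0.50.

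The cost is a few sentences in each document and a less favourable stated figure. Enrolment, endpoints and analyses do not change.
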